## Statistical Analysis Plan for 1820202

level, then a linear regression on response will be performed with categorical dose as the predictor. An unstratified logistic regression analysis may still be used to explore the dose-response relationship.

[figure not shown]

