### **9.3.1. Efficacy Analyses**

Unless otherwise noted, baseline for all efficacy assessments for GL refers to the last available assessment prior to GL treatment for those associated with GL severity and for FHL refers to the last available assessment prior to FHL treatment for those associated with FHL severity.

The primary efficacy endpoint will be the proportion of subjects achieving a score of 0 or 1 (none or mild) on the FHWS as assessed by IGA-FHWS at maximum eyebrow elevation at Week 6. The dose response in the proportion of responders at 4 weeks after the FHL treatment (Week 6) will be explored using the logistic regression stratified by baseline FHWS severity (last assessment prior to GL treatment at Day 1 Visit) and study center to assess the dose-response. Additional measures to assess the effectiveness outcomes will include the IGA-FHWS, PFHWS, GAIS evaluated at maximum contraction (eyebrow elevation) and at rest at each visit. Various responder endpoints associated with the FHWS, such as achieving certain status or certain magnitude of improvement from baseline, will be derived from these effectiveness outcomes for each visit. These responder endpoints will be analyzed by statistical models similar to that for the primary endpoint.

Duration of response will be evaluated by various time-to-event endpoints. Kaplan-Meier curves will be plotted by dose group for each time-to-event endpoint and median duration with associated 95% CIs will be provided.

Similar responder and time-event endpoints associated with the GL wrinkle severity defined based on the assessments for GL wrinkle severity such as IGA-FWS, PFWS or GAIS on GL, will be summarized similarly to those endpoints associated with FHWS. Efficacy outcomes will be summarized. Descriptive statistics will be provided for all efficacy variables at all timepoints. Note that exploratory analyses of the change in FHL severity from Day 1 (post-GL treatment) to Week 2 and from pre-FHL treatment (Week 2 pre-treatment) to post treatment will also be performed.

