### 6.5.1 Primary Efficacy Analysis

The proportion of subjects achieving a score of 0 or 1 (none or mild) on the IGA-FHWS at maximum eyebrow elevation at Week 6 will be summarized. Subjects with no data at Week 6 after imputation of worst value will be considered to not meet the criteria (i.e., are imputed as non-responders). An exact 95% confidence intervals for the individual proportions will also be provided. A Cochran-Mantel-Haenszel test of association, stratified by stratified by baseline IGA-FHWS severity and study center, will be performed. In addition, an exact Cochran-Armitage test for trend, ignoring the stratification factors, will be performed. If the Cochran-Mantel-Haenszel test is significant at the 0.05 significance

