## 6.7 Changes from the Planned Analyses

The primary analysis to explore dose response was planned to be an exact logistic regression stratified by study center and baseline severity, however, the conditional distribution is degenerate. A logistic regression may still be performed, but the primary analysis has been changed to a Cochran-Mantel-Haenszel statistic supplemented with the Cochran-Armitage test for trend. If the Cochran-Mantel-Haenszel test is significant, then a linear regression with dose as the predictor will be performed.

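### The only dose-response model that SAP 6.5.1 commits to is a linear regression of a yes/no outcome on categorical dose, run only when the CMH test is significant

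*SAP*

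**What the plan says.** The primary efficacy outcome is yes/no for each subject. SAP 6.5.1 summarizes "The proportion of subjects achieving a score of 0 or 1 (none or mild) on the IGA-FHWS at maximum eyebrow elevation at Week 6", with an exact 95% interval for each cohort's proportion.

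For dose response, SAP 6.5.1 then lists:

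- A stratified test: "A Cochran-Mantel-Haenszel test of association, stratified by stratified by baseline IGA-FHWS severity and study center, will be performed".
- A trend test: "an exact Cochran-Armitage test for trend, ignoring the stratification factors, will be performed".
- A conditional model. The condition is "If the Cochran-Mantel-Haenszel test is significant at the 0.05 significance" level; the consequence is "then a linear regression on response will be performed with categorical dose as the predictor".
- An optional model: "An unstratified logistic regression analysis may still be used to explore the dose-response relationship".

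Three other places bear on this:

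- Protocol 9.3.1 set no condition. The dose response "will be explored using the logistic regression stratified by baseline FHWS severity" and study center.
- SAP 6.7 says that the stratified exact logistic regression was replaced because its conditional distribution is degenerate. It restates the conditional model without the word categorical: "then a linear regression with dose as the predictor will be performed".
- SAP 6.5.4 still states that the primary endpoint needs the stratified exact logistic model.

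The visible SAP text gives no degrees of freedom for the CMH test, and no variance estimator or interval method for the linear regression.

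**The concern.** A phase 2a dose-escalation study is normally read for how response changes with dose. Three features of the rule work against that.

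1. **The gate.** A significance test decides whether a modelled estimate is produced, in a study whose sample size is not based on power (SAP 3.1.1) and whose tests are exploratory (Protocol 9.3). When the gate stays shut, no committed model describes the dose response. When it opens, the contrasts shown come from trials selected for large observed differences.
2. **The model.** Least squares with one common variance does not suit a binary outcome when cohort rates differ and approach 100%. With four dose categories the fit reproduces the four cohort proportions: three contrasts and no slope.
3. **The text.** SAP 6.5.1, 6.5.4 and 6.7 describe different models for the same question, so two programmers could follow the SAP and report different things.

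At stake is the usefulness of the dose-response summary for later dose selection. No confirmatory claim is at stake.

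**Working it through.** **Inputs from the documents.** Four cohorts of 15 (Protocol 4.1), so 4 × 15 = 60, which matches the planned total. Four sites and two baseline severities (moderate, severe) give 4 × 2 = 8 strata, or 60/8 = 7.5 subjects per stratum. Crossed with four cohorts that is 32 cells, or 60/32 ≈ 1.9 subjects per cell. The plan gives no power or effect-size figure to reproduce.

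**Assumptions.** The documents give no expected response rates, so a range is used. The CMH test is taken as the 3-df general-association form; the 1-df ordered form is also shown. Site is assigned at random and severity is balanced.

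**Step 1: the gate.** Each scenario has 6,000 simulated trials. D is the top-cohort minus bottom-cohort proportion. In the categorical model this equals the raw difference in proportions. Inflation is the mean of D in CMH-significant trials divided by the true D.

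| Assumed rates (%) | True D | Gate opens, 3 df | Mean D when open | Inflation | Gate opens, 1 df |
|---|---|---|---|---|---|
| 80/85/90/95 | 0.15 | 11% | 0.268 | 1.79 | 21% |
| 70/80/90/95 | 0.25 | 27% | 0.367 | 1.47 | 48% |
| 60/70/80/90 | 0.30 | 28% | 0.430 | 1.43 | 47% |
| 50/65/80/95 | 0.45 | 65% | 0.514 | 1.14 | 84% |
| 30/50/70/90 | 0.60 | 86% | 0.634 | 1.06 | 95% |

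For example, 0.430/0.30 = 1.43. Repeat simulations put the gate at 28% to 30% for 60/70/80/90% and the inflation in the flattest scenario at up to about 1.9. Without the gate, D is essentially unbiased: 0.297 against 0.30, 0.148 against 0.15, and 0.452 against 0.45. The 1-df form opens more often but still selects: for 60/70/80/90% the mean is 0.407, and 0.407/0.30 = 1.36.

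**Step 2: a single data set.** Take 10, 12, 14 and 15 responders of 15. The unstratified 3-df test gives p = 0.055, and the exact Cochran-Armitage test gives p = 0.008. On the unstratified test, a clear monotone trend would leave the regression unrun. The stratified result depends on how responders fall across strata.

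**Step 3: intervals, if ordinary pooled-variance least squares is used.** For the same counts:

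- Residual sum of squares, Σ 15·p(1−p) = 3.333 + 2.400 + 0.933 + 0 = 6.667
- Mean square = 6.667/56 = 0.1190
- Standard error of a cohort mean = √(0.1190/15) = 0.0891
- Half-width = 2.003 × 0.0891 = 0.178

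The 15/15 cohort gets 82% to 118%. The exact interval is 78% to 100%, with lower limit 0.025^(1/15) = 0.782. With 9, 12, 14 and 15 responders (unstratified p = 0.019, gate open) the least-squares interval is again 82% to 118%.

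Enumerating all 16⁴ outcomes gives the coverage of nominal 95% least-squares intervals for pairwise differences. Coverage is 95.0% when all rates are 90%, and 87.3% to 99.9% when rates differ. For 50/65/80/95% it is 90.0% for cohort 1 versus 2 and 99.0% for cohort 3 versus 4. Newcombe intervals covered 93.6% to 99.9% in the same scenarios. A least-squares limit for at least one cohort passes 0 or 1 in 97% to 100% of trials when rates differ.

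**Step 4: what is reported without the gate.** The cohort proportions with exact intervals and the Cochran-Armitage p-value are committed and unconditional. The logistic model is unconditional but optional. SAP 6.5 adds that between-cohort differences are shown only where the table shells call for them. The model in SAP 6.5.4 cannot fill the gap, because SAP 6.7 reports it as degenerate.

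**The case against.** The strongest reply is that the gate hides little. The categorical model only reproduces the four cohort proportions, and these appear with exact intervals whatever the CMH result. A reader can subtract them. The trend test is ungated, and nothing forbids the logistic model. The protocol calls dose response exploratory and plans no formal tests. The move away from exact logistic regression is disclosed and explained in SAP 6.7.

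Most of this stands, and it rules out several stronger readings:

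- **That the study usually reports no estimate of response by dose.** The cohort estimates always appear. How often the gate opens also depends on assumed rates and on an unstated CMH form: 11% to 86% with 3 df.
- **That an inflated slope is reported.** Under SAP 6.5.1 there is no slope. Slope inflation could arise only under SAP 6.7, if dose there means numeric dose. The figures above are therefore for a contrast.
- **That the intervals are invalid.** The SAP specifies none for this regression. Pooled least squares would be miscalibrated in both directions, and correct when rates are equal.
- **That a confirmatory conclusion is at risk.** None is planned.

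What the reply does not answer is that the trend test gives only a p-value, the logistic model may never be run, and three sections of one SAP disagree on the model.

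**Conclusion.** The point holds as a should-fix on an exploratory analysis. The one dose-response model that is both committed and executable is gated on significance, fitted by a method poorly suited to a binary outcome, and coded so that it yields no slope. Under the assumed rates and a 3-df test, the gate opens in 11% to 86% of trials. The difference shown when it opens is inflated by about 6% to 90%, most when the true dose response is shallow. The inflation applies to a reader who relies on the regression output; the ungated cohort proportions are unaffected. The interval figures apply only if ordinary pooled-variance least squares is used. The disagreement among SAP 6.5.1, 6.5.4 and 6.7 rests on no assumption.

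**What to change.** 1. Remove the significance condition, and delete the linear regression from SAP 6.5.1 and 6.7.
2. Always report one pre-specified logistic model of Week 6 response, with FHL dose as a numeric or ordered term and baseline IGA-FHWS severity as a covariate. Firth penalization is one suitable choice, because it still gives finite estimates when a cohort has 0% or 100% responders.
3. Report the odds ratio with its 95% interval and the fitted response at each dose, beside the exact cohort intervals. If pairwise differences are wanted, use a score-based interval such as Newcombe's.
4. Protocol 9.3.1 includes study center. State that it is left out because the strata are sparse, or add it in a sensitivity analysis.
5. Align SAP 6.5.1, 6.5.4 and 6.7 on this model, and state the form and degrees of freedom of the CMH test.

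The cost is SAP wording and one standard procedure option, with no change to data collection. The small downside is that a numeric dose term assumes linearity in the log-odds; the cohort proportions beside it let readers check that.

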#### **6.5.3.1 Proportions of Subjects Meeting a Given Criterion**

The assessments of the proportion of subjects meeting a given criterion (“responders”) will be summarized by summary cohort and visit. For each endpoint at selected visits, the point estimates and exact 95% CIs will be computed using the same methods as with the primary endpoint.

The proportion of responders will also be graphically displayed in a plot with time on the x-axis and the proportion of subjects responding on the y-axis.

#### **6.5.3.2 Time to Return to, or Time to Loss of, a Given State**

The time to return to a given state, or time to loss of a given criterion, will be summarized with point estimates of median duration and 2-sided, 95% CIs, using the log-log transformation by summary cohort. Estimates of survival rates and the 2-sided, 95% CI, using the log-log transformation will also be provided. Kaplan-Meier survival curves will be plotted such that each summary group is a separate line in the same plot.

#### 6.5.3.4 Descriptive Statistics and Change from Baseline

Responses to the FASE questionnaire at the Week 2 study visit, actual age, number of years older, younger will be descriptively summarized.

Transformed scores for the FACE-Q™ Satisfaction with Forehead and Eyebrows and the FACE-Q™ Appraisal of Lines: Forehead will be summarized using descriptive statistics for continuous variables.

#### 6.5.4 Adjustments for Covariates

The analysis of the primary endpoint requires a stratified exact logistic regression model be run, where the strata are created based on the baseline IGA-FHWS severity and study site, both of which are considered to be covariates.

[REDACTED]

### 6.6 Safety Analyses

Safety summaries and analyses will be performed on the Safety and Safety FHL populations and will be presented by cohort and in total across cohorts. Descriptive statistics will be presented to summarize the safety data. By visit safety summaries will use denominators based on the number of subjects with valid observations at that visit unless otherwise specified.

#### 6.6.1 Extent of Exposure

All subjects are planned to receive two treatments of investigational product (GL, FHL treatments). The dosage of investigational product injected and the dose of investigational product injected at each of the injection sites will be summarized overall and by summary cohort for each administration using

## Statistical Analysis Plan for 1820202

descriptive statistics (number of non-missing observations, mean, median, first and third quartiles, minimum, maximum, and standard deviation).

### 6.6.2 Injection Site Evaluations

The injection site evaluations for GL and FHL will be summarized separately using number and percentage of subjects with a reaction at any post-treatment visit. In addition, the number and percentage of subjects experiencing an AE of special interest related to GL injection site reactions and FHL injection site reactions will be summarized by summary cohort, system organ class, and preferred term.

### 6.6.3 Adverse Events

All AEs will be recorded and classified on the basis of MedDRA terminology. All treatment-emergent AEs will be summarized by summary cohort and overall, system organ class, preferred term, severity, and seriousness. When summarizing events by causality and severity by subject, each subject will be counted only once within a system organ class or a preferred term by using the event with the greatest relationship and highest severity within each classification. Additionally, some summaries will present the number of AEs as well as incidence.

An overall summary of treatment-emergent AEs (TEAEs) will be provided. The number and percentage of subjects experiencing an AE, an SAE, a related AE, a related SAE, an AE of special interest, an AE leading to study discontinuation, and an AE resulting in death will be summarized.

All information pertaining to AEs noted during the trial will be listed by subject, detailing the verbatim description given by the Investigator, preferred term, system organ class, start date, stop date, severity, action taken regarding trial drug, corrective treatment, outcome, and drug relatedness. The event onset relative (in number of days) to the date of treatment for GL and FHL, as well as to the date of last treatment administration prior to the event, will be provided. In addition, a list of adverse events that lead to the subject's premature discontinuation of the trial will be provided. Serious adverse events (SAEs) will be listed by subject.

Statistical Analysis Plan for 1820202

## 6.6.4 Laboratory Tests

[figure not shown]
### 6.6.4.1 Clinical Safety Laboratory Parameters

Laboratory test results will be summarized with descriptive statistics by visit. Change from baseline to post-baseline visits will be summarized for continuous test results. A summary of abnormal urinalysis incidence will be presented displaying normal, abnormal (not clinically significant), and abnormal (clinically significant) results.

Shift tables will be presented to summarize laboratory test results at Baseline and Final Evaluation Visit. Normal ranges established by the central laboratory will be used to determine shifts. A listing of all out-of-range laboratory test results at any evaluation will also be provided. Determination of clinical significance for all out-of-range laboratory values will be made by the investigator and included in the listing. In addition, a listing of all clinically significant laboratory test results will be provided.

### 6.6.4.2 Pregnancy Tests

Urine pregnancy tests will be presented in data listings for all treated subjects in the category of woman of child-bearing potential.

## 6.6.6 Vital Signs and Physical Examination

Vital signs and ECG parameters will be summarized by cohort with descriptive statistics by visit. Vital signs and ECG parameters will summarize the actual value as well as the change from baseline for each visit for continuous parameters.

Abnormal findings from the physical examination will be summarized by body system and cohort using number and percentage of subjects with a normal, abnormal and clinically significant, or abnormal and not clinically significant result.

## 6.7 Changes from the Planned Analyses

The primary analysis to explore dose response was planned to be an exact logistic regression stratified by study center and baseline severity, however, the conditional distribution is degenerate. A logistic regression may still be performed, but the primary analysis has been changed to a Cochran-Mantel-Haenszel statistic supplemented with the Cochran-Armitage test for trend. If the Cochran-Mantel-Haenszel test is significant, then a linear regression with dose as the predictor will be performed.
